## 6.3 Measures to Minimize Bias: Randomization and Blinding

On Day 1, participants will be assigned a unique number (randomization number) in ascending numerical order at the study site. The randomization number encodes the participant's assignment to one of the seven (7) arms of the study, according to the randomization schedule generated prior to the study by the Sponsor. Each participant will be dispensed blinded study intervention, labeled with his/her unique randomization number, throughout the study.

Participants enrolled in the trial, investigators and their staff involved in protocol procedures or who are involved in data collection, data entry and data analysis will be blinded to the

identity of the treatments until the database is locked. The study monitor will conduct product accountability after database lock. To preserve blinding, participants will be blindfolded during administration of study medication. Study drug will be dispensed by an unblinded study team member based on the randomization schedule. That team member may have no other role in the study conduct and may not reveal the study drug's identity to any members of the blinded study team.

Sponsor will supply study medication in bulk containers. Selection of the proper dose for an individual participant will be performed by an unblinded study team member using the provided randomization schedule. The unblinded study team member will withdraw the appropriate study medication from the bulk container and transfer it to a dispensing cup. All study interventions must be administered as 2 tablets per participant. Some study interventions require the addition of a placebo tablet. The unblinded study team member will then bring the study medication to the treatment room where it will be dispensed to the participant by the study team member. The unblinded study team member should have no other responsibilities in the study.

### **6.3.1 Unblinding**

In the case of a medical emergency, such as serious adverse events (SAE), breaking the blind may become necessary during the trial

In compliance with applicable regulations, in the event of a serious unexpected adverse event (SUSAR) related to the blinded treatment, the participant's treatment code will usually be unblinded before reporting to the health authorities, ethic committees and investigators (see Section 8.3.5).

### **6.3.2 Emergency unblinding by the investigator**

The investigator must report the blind break in conjunction with a SAE within 24 hours of becoming aware of the effect as defined in Section 10.3.1. Participants who have been unblinded will not be included in the ITT or PP efficacy analysis.

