#### Follow-Up Phase

Participants will be evaluated at a post-operative visit/call approximately 2-5 days after discharge for follow up for any adverse events or medications not known at the time of treatment.

The duration of each participant's participation will be approximately 37 days. For an overview on the study design and study procedures (see [Figure 1](#)).

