### **6.7 Intervention after the End of the Study**

This study is a single dose administration after surgery and there is no additional treatment allocated. Participants who randomize into the study will be discharged from the study center after the final (12 hour post dosing) assessments, regardless of whether rescue medication had been taken or not.

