### 9.3 Populations for Analyses

For purposes of analysis, the following populations are defined:

Population	Description
Safety	All participants who are randomized and take at least one dose of investigational product. Safety measures will be analyzed for all participants in the safety population.
Intent-To-Treat (ITT)	All participants in the Safety Population who provide at least one pain assessment after the first dose of the investigational product. ITT population will be used as secondary to conduct the sensitivity analysis for the selected parameters.
Per Protocol (PP) Population	
PP population will include all participants in ITT who do not have any major protocol violations and complete the 12 hour assessments. PP population will be used as the primary analysis for the efficacy parameters.
 
Major protocol deviations will be identified prior to database lock and may include but are not limited to significant violations of inclusion/exclusion criteria, noncompliance of the trial treatment taken, conditions such as vomiting and diarrhea or use of prohibited medications, and not following clinical trial protocol procedures. Any participant who rescues or vomits at or prior to 60 minutes after ingesting study medication will be excluded from the PP population.

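### Protocol 6.3.2 removes unblinded participants from ITT and PP whatever the time of the code break, contradicting the ITT definition in 9.3 and dropping ratings already made under blind

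*Protocol*

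**What the plan says.** Protocol 6.3.2, under emergency unblinding by the investigator, says: "Participants who have been unblinded will not be included in the ITT or PP efficacy analysis". No time of break and no exception is given.

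Protocol 9.3 defines ITT as "All participants in the Safety Population who provide at least one pain assessment after the first dose of the investigational product". It mentions neither unblinding nor 6.3.2. On the role of the set it says: "ITT population will be used as secondary to conduct the sensitivity analysis for the selected parameters". PP is the primary efficacy set and is drawn from ITT: "PP population will include all participants in ITT who do not have any major protocol violations and complete the 12 hour assessments". The list of major deviations is left open: "Major protocol deviations will be identified prior to database lock and may include but are not limited to significant violations of inclusion/exclusion criteria".

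On timing, Protocol 6.7 has participants "discharged from the study center after the final (12 hour post dosing) assessments", and the Follow-Up Phase text in 4.1 adds: "Participants will be evaluated at a post-operative visit/call approximately 2-5 days after discharge". Protocol 8.3.1 collects adverse events, serious ones included, up to that follow-up. Protocol 6.3.1 allows the blind to be broken in a medical emergency during the trial. It adds that for a SUSAR the "treatment code will usually be unblinded before reporting to the health authorities, ethic committees and investigators".

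The SAP's population section (6.4) is redacted. SAP 6.3 says that deviations leading to exclusion will be identified and summarised, but not whether a code break counts as one.

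**The concern.** Two statisticians working from the protocol could build different ITT sets from the same data, one following 9.3 and the other 6.3.2.

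The content of the 6.3.2 rule is also a problem. Pain is self-rated, so a code break can influence ratings made after it but not ratings made before it. A rule that ignores the time of the break removes both kinds. The exclusion is made after randomisation, and its trigger is an emergency, typically a serious adverse event, that the assigned treatment may have caused. Selection of that kind is what an ITT sensitivity analysis is meant to expose. Here it cannot, because the same people are taken out of both sets.

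**Working it through.** **1. Do the two sections conflict?** Take a participant who is dosed, gives every rating to hour 12, and has the code broken by the investigator the next day.

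- ITT under 9.3: included (dosed, with post-dose ratings). ITT under 6.3.2: excluded. This is a contradiction.
- PP under 9.3: included unless the break is classed as a major deviation, which the open-ended list permits. PP under 6.3.2: excluded. These can be reconciled.

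The direct contradiction is therefore confined to ITT. Because PP is a subset of ITT, removal from ITT also forces removal from the primary set.

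**2. Can a break fall after the last rating?** Ratings end at hour 12 and discharge follows (6.7). Safety collection continues to the follow-up contact (4.1, 8.3.1), and 6.3.1 allows a break during the trial. So it can. Nothing in the documents says how often.

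**3. What leaves the efficacy analysis?** The post-dose times are 0.5, 1, 1.5 and 2 hours (4 ratings) and hourly from 3 to 12 (10 ratings): 4 + 10 = 14. Those up to hour 8 number 4 + 6 = 10, and these make up SPID0-8. With a break after hour 12, all 14 were made under blind.

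**4. Can ITT show the effect?** Under 6.3.2 an unblinded participant is in neither set. Any difference between the ITT and PP results then reflects only the other PP exclusions.

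**5. Size of one removal.** First, the plan's own figures. The 2:2:2:2:2:1:1 ratio in 6.1.1 sums to 12 and 180/12 = 15, so arms are 30 or 15 and 5 × 30 + 2 × 15 = 180. With 5% dropout, 180/0.95 = 189.47, rounded up to 190, which agrees with 9.2.

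Share of an arm: 1/30 = 3.3%; 1/15 = 6.7%.

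The standard error of a two-arm difference is proportional to √(1/n₁ + 1/n₂), assuming a common SD. Ratios after losing one participant:

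- 30 vs 30: √(1/29 + 1/30) / √(1/30 + 1/30) = 1.009, up 0.9%
- 30 vs 15, lost from the 30: √(1/29 + 1/15) / √(1/30 + 1/15) = 1.006, up 0.6%
- 30 vs 15, lost from the 15: √(1/30 + 1/14) / √(1/30 + 1/15) = 1.024, up 2.4%

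Removing one participant whose SPID0-8 lies D units from the arm mean moves that mean by D/(n − 1). D is not known. For assumed values of 10 to 40, the shift is 0.34 to 1.38 units in an arm of 30 and 0.71 to 2.86 in an arm of 15, in either direction.

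**6. Frequency.** No code-break rate is given. For assumed rates of 0.1%, 0.5% and 1%, the expected number among 180 is 0.18, 0.9 and 1.8.

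**The case against.** The strongest reply is that this will seldom matter. It is a single-dose study in healthy volunteers, 9.2 says it is not powered, and one removal costs little precision. That stands, and it limits the size of the point. It does not settle which ITT set is meant.

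A second reply is that the SAP may already resolve the matter, since Protocol 9.4 leaves the populations to it. SAP 6.4 and most of SAP 8 are redacted, so this cannot be checked, and nothing is claimed about their content. The two readable protocol sections still disagree.

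A third reply is that ratings made after a break are suspect. That is fair for breaks before hour 12 and supports a PP exclusion there. It does not apply to ratings completed before the break.

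Stronger readings go further than the documents allow:

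- A reader might infer that most breaks would come after hour 12, because follow-up lasts days. The documents give no timing of breaks. They also anchor the contact differently: after discharge in 1.3 and 4.1, after surgery in 4.4. Elapsed time says nothing about how many breaks fall in it.
- A reader might infer that the data are lost. They leave the efficacy analysis only; the scores stay in the database and the participant stays in the Safety Population.
- A reader might infer that SUSAR code breaks by the sponsor are covered. The sentence is general, but it sits under investigator unblinding, so its reach is unclear. Likewise, the 8.3.1 duty concerning events learned of after discharge is to notify the sponsor; it does not mention breaking the code.
- A reader might infer that the ITT-versus-PP contrast would become informative for late breaks once the rule is corrected. It would not, since those participants would be in both sets. The contrast helps only for earlier breaks.

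**Conclusion.** The point holds. Protocol 6.3.2 and 9.3 cannot both define the ITT efficacy set, and 6.3.2 as written removes blinded ratings because of a later post-randomisation event. The conclusion rests on the protocol text alone, and an investigator break after hour 12 is enough to establish it.

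The expected effect is small: per removal, the figures in step 5, on planned evaluable arm sizes and a common SD. The direction of any bias is unknown, and the documents do not show that a late break is likely. The reason to correct it is that the exclusion may be related to treatment, the planned sensitivity analysis cannot reveal its effect, and the correction is cheap.

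**What to change.** - In Protocol 6.3.2, delete the ITT exclusion so that 9.3 governs. Unblinded participants then stay in ITT with their recorded scores, under the same rescue and missing-data rules as everyone else. The rescue imputation in 9.4.1 does not cover scores missing because an unblinded participant withdrew, so those must fall under the general missing-data rule (SAP 6.1.5, partly redacted).
- In Protocol 9.3, make a code break a reason for PP exclusion only if it occurred before the 12-hour assessments were completed. This needs the time of the break to be on record.
- State whether code breaks by the sponsor for SUSAR reporting are covered.
- Check that the SAP population definitions agree, and say whether a code break counts as a deviation under SAP 6.3.

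The cost is an edit to one sentence in 6.3.2, an added sentence in 9.3, a short clarification on SUSAR breaks, and a SAP check. Planned numbers stay at 180 evaluable and 190 randomised, no analysis is added, and the rules on when the blind may be broken are untouched. The downside is that a few scores recorded after a code break may remain in the ITT sensitivity analysis.

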## **6.4 Study Intervention Compliance**

The administration of the study medication will be supervised by an unblinded member of the Investigator's team. This person will perform the oral cavity inspection after study drug administration and document that the participant receives the treatment as planned.

## **6.5 Prior and Concomitant Therapy**

The following treatments are prohibited from screening and during the study:

- Use of any form of medication or herbal supplements, including GABA and turmeric, or curcumin, within 5 days of surgery that would confound the evaluation of the study product, until discharge from the study site;
- Use of acetaminophen, naproxen, hydrocodone/acetaminophen, ibuprofen, aspirin, or other NSAIDs or any other pain reliever (OTC or prescription) within 5 days before surgery;

- Use of alcoholic beverages after midnight prior to surgery and throughout the evaluation period;

All medications (prescription and nonprescription products, vitamin and herbal products) taken by the participant from 30 days prior to Screening to End of Trial (EOT) will be documented. The reported medications will be reviewed and evaluated by the Principal Investigator or designee to determine if they affect the participant's eligibility to participate in the study.

### **6.5.1 Rescue Medicine**

If adequate pain relief was not achieved, then participants are permitted to take rescue medication, although they will be encouraged to wait 2 hours to allow the investigational product time to take effect. The study site will supply the rescue medication that will be obtained locally. Rescue medication will be Hydrocodone 5 mg/Acetaminophen 325 mg tablets or other appropriate analgesics may be used at the discretion of the Investigator. Rescue medication is also available on return of pain and the time of rescue medication will be recorded. Pain assessments will be performed immediately before the first dose of rescue medication.

- Rating of Pain Intensity (NRS);
- Rating of Pain Relief (Categorical);
- Global Assessment of investigational product as a pain reliever.

All active stopwatch elapsed time(s) will be stopped at the time of rescue administration and recorded on the case report form.

Participants will be queried in a nonspecific fashion for any adverse events. All observed and reported AEs will be collected and recorded on the case report form. The information recorded will be based on signs and symptoms reported by the participant or observed by the research coordinator during clinical evaluation.

### **6.6 Dose Modification**

The dosing schedule cannot be modified.

### **6.7 Intervention after the End of the Study**

This study is a single dose administration after surgery and there is no additional treatment allocated. Participants who randomize into the study will be discharged from the study center after the final (12 hour post dosing) assessments, regardless of whether rescue medication had been taken or not.

## **7. Discontinuation of Study Intervention and Participant**

### **7.1 Discontinuation of Study Intervention**

See the SoA for data to be collected at the time of intervention discontinuation and follow-up and for any further evaluations that need to be completed.

## 7.2 Participant Discontinuation/Withdrawal from the Study

### Withdrawal criteria

Participants *must* be withdrawn from the study if any of the following occurs:

- A participant may withdraw from the study at any time at his/her own request, or may be withdrawn at any time at the discretion of the investigator for safety, behavioral, compliance, or administrative reasons. This is expected to be uncommon.
- At the time of discontinuing from the study, if possible, an early discontinuation visit should be conducted, as shown in the SoA. See SoA for data to be collected at the time of study discontinuation and follow-up and for any further evaluations that need to be completed.
- The participant will be permanently discontinued both from the study intervention and from the study at that time.
- If the participant withdraws consent for disclosure of future information, the sponsor may retain and continue to use any data collected before such a withdrawal of consent.
- Participant's pain intensity post-surgery at pre-dose does not exceed 'mild' and the NRS is <5 (see Section 10.5);
- If, in the Investigator's opinion, continuation of the study would be harmful to the participant's well-being;

Participants *may* be withdrawn from the study if any of the following occurs:

- Participant experiences one or more serious adverse events;
- At the specific request of the Sponsor and in consultation with the Investigator (e.g., obvious non-compliance, safety concerns);
- Protocol violation: if the participant develops conditions, which would have prevented his/her entry into the study according to the inclusion/exclusion criteria, he/she must be withdrawn immediately if safety is concerned; in other cases, the investigator will decide whether there is a conflict with the study objectives.

## 7.3 Lost to Follow Up

A participant will be considered lost to follow-up if he or she repeatedly fails to return for scheduled visits and is unable to be contacted by the study site.

The following actions must be taken if a participant fails to return to the clinic for a required study visit:

- The site must attempt to contact the participant and reschedule the missed visit as soon as possible and counsel the participant on the importance of maintaining the assigned visit schedule and ascertain whether or not the participant wishes to and/or should continue in the study.
- Before a participant is deemed lost to follow up, the investigator or designee must make every effort to regain contact with the participant (where possible, 3 telephone calls and, if necessary, a certified letter to the participant's last known mailing address

or local equivalent methods). These contact attempts should be documented in the participant's medical record.

- Should the participant continue to be unreachable, he/she will be considered lost to follow up.

## 8. Study Assessments and Procedures

Study procedures and their timing are summarized in the SoA. Protocol waivers or exemptions are not allowed. Immediate safety concerns should be discussed with the sponsor immediately upon occurrence or awareness to determine if the participant should continue or discontinue study intervention. Adherence to the study design requirements, including those specified in the SoA, is essential and required for study conduct.

All screening evaluations must be completed and reviewed to confirm that potential participants meet all eligibility criteria. The investigator will maintain a screening log to record details of all participants screened and to confirm eligibility or record reasons for screening failure, as applicable.

Procedures conducted as part of the participant's routine clinical management (e.g., blood count) and obtained before signing of the ICF may be utilized for screening or baseline purposes provided the procedures met the protocol-specified criteria and were performed within the time frame defined in the SoA.

### 8.1 Efficacy Assessments

If not stated otherwise, the measures / actions listed in the following Sections 8.1.1 to 8.1.6 will be performed by a designated study team member as designated by the Principal Investigator.

#### 8.1.1 Screening Period

**Note: No screening procedures may be performed unless participants have been provided an IRB-approved written informed consent which participants have read, understood, and signed.**

The Screening Period will be up to 28 days long. The following will be determined during the Screening Visit:

- Signed Informed Consent Form (ICF);
- Review inclusion and exclusion criteria;
- Participant demographics;
- Medical/surgical history including history of drug, alcohol, tobacco and caffeine use;
- Medication history of all prescription, OTC products including vitamins or dietary/herbal supplements, taken during the past 30 days;
- Vital signs consisting of sitting blood pressure (in triplicate with one min in between), respiratory rate and pulse after sitting for at least 5 minutes;

- Physical and oral examination;
- Dental x-ray examination and interpretation including impaction score;  
Note: The medical interpretation may occur after the screening visit provided a diagnosis of impaction is determined prior to surgery.
- Urine tests for illicit drugs;
- Breath or saliva alcohol test;
- Urine pregnancy test (if applicable).

Upon satisfying the inclusion/exclusion criteria, eligible participants will be instructed to return to the trial site within 28 days for oral surgery. Participants will be instructed to refrain from the use of all medications (prescription, nonprescription, herbal supplements) unless in the opinion of the Investigator or Sponsor, the medication will not interfere with study procedures, data integrity, or compromise the safety of the participants.

Participants will be instructed not to consume alcohol or use any nicotine containing products 24 hours prior to surgery. Surgery will be scheduled between 0530 h and 1030 h.

The Principal Investigator or his/her designee must review participant's study records before qualifying the participant for the trial.

### **8.1.2 Pre-surgery**

Participants are instructed to be nil per os (NPO) from midnight prior to surgery. If a participant had something to eat or drink after midnight, the surgeon must determine if surgery may proceed. Participants will arrive at the unit at their assigned time and will have the following activities completed prior to dental surgery:

- Review changes in the participant's medical/medication history and inclusion/exclusion criteria since previous visit;
- Urine tests for illicit drugs;
- Breath or saliva alcohol test;
- Vital signs consisting of sitting blood pressure (in triplicate with one min in between), respiratory rate and pulse after sitting for at least 5 minutes;
- Urine pregnancy test (if applicable);
- Review pain assessment process and procedures.

### **8.1.3 Impaction Score**

An Impaction Score will be used to assess each tooth based on the radiographic appearance and the intraoral examination. Each tooth will be rated from 1 to 4 using the following criteria: (1) erupted in tissue (2) soft tissue impaction (3) partial bony impaction, and (4) full bony impaction. Only participants whose mandibular impactions are scored (3) or (4) will be eligible to participate in the study.

